Thromboembolic events are frequent in cancer patients due to procoagulant changes induced by the malignancy or anti-cancer therapy. Deep vein thrombosis and PE have been observed in clinical studies with cabozantinib; including fatal events (please refer to the Investigator's Brochure). Subjects who develop a PE and/or DVT should have cabozantinib treatment held until therapeutic anticoagulation with heparin (eg, LMWH) is established. (Note: Therapeutic anticoagulation with oral anticoagulants or oral platelet inhibitors such as clopidogrel is not allowed in this study). Cabozantinib treatment may be resumed in subjects with PE or DVT if it is determined that the event is uncomplicated, they are deriving benefit from study treatment, and that anticoagulation does not place them at a significant risk that outweighs the benefit of resuming treatment. During anticoagulation treatment, subjects need to be monitored on an ongoing basis for bleeding risk and signs of bleeding which may require additional or more frequent laboratory tests according to institutional guidelines. Results of such tests are to be forwarded to the local laboratory data management vendor. If there are any signs of clinically relevant bleedings, cabozantinib treatment should be interrupted immediately. Subjects with life-threatening PE or DVT should have study treatment discontinued unless toxicity can be managed and subject is deriving clear clinical benefit as determined by the investigator.

observed in studies with cabozantinib. Subjects should be evaluated for pre-existing risk factors for arterial thrombotic events such as diabetes mellitus, hyperlipidemia, hypertension, coronary artery disease, history of tobacco use, and cardiac and/or thromboembolic events that occurred prior to initiation of study treatment. Cabozantinib treatment should be discontinued in subjects who develop an acute myocardial infarction, cerebral infarction or any other clinically relevant arterial thromboembolic complication.

PROTEINURIA

Proteinuria has been reported with cabozantinib. Proteinuria should be monitored by measuring UPCR. Table 8 provides treatment guidelines for proteinuria deemed related to cabozantinib.

Cabozantinib should be discontinued in subjects who develop nephrotic syndrome (proteinuria > 3.5 grams per day in combination with low blood protein levels, high cholesterol levels, high triglyceride levels, and edema) or any other relevant renal disease.

Table 8: Management of Treatment associated Proteinuria

Severity of	Action To Be Taken
Proteinuria (UPCR)	
≤ 1 mg/mg (≤ 113.1 mg/mmol)	-- No change in cabozantinib treatment or UPCR monitoring
> 1 and < 2.0 mg/mg (> 113.1 and < 226.2 mg/mmol)	-- No change in cabozantinib treatment -- Consider confirming with a 24-hour urine protein assessment within 7 days (+/- 3 days). -- Consider monitoring UPCR once every week (+/- 3 days until UPCR < 1 on 2 consecutive readings, UPCR monitoring can revert to protocol-specific times.
≥ 2.0 mg/mg (≥ 226.2 mg/mmol)	-- Hold cabozantinib treatment pending repeat UPCR and/or 24-hour urine protein. -- If ≥ 2.0 on repeat (UPCR or 24-hour protein), continue to hold cabozantinib treatment and check UPCR every week (+/- 3 days). If UPCR decreases to < 2 , restart cabozantinib treatment at a reduced dose and continue monitoring UPCR once weekly (+/- 3 days) until the UPCR decreases to < 1 .
Nephrotic syndrome	Discontinue cabozantinib treatment

CORRECTED QTc PROLONGATION

In accordance with clinical practice ECGs will be collected during this study. Only subjects with a baseline QT corrected by Fridericia (QTcF) ≤ 500 ms are eligible for this study. Subjects will have ECGs performed at times designated by the protocol: triplicate at screening, and single ECGs at monthly visits.

If at any time on study there is an increase in QTcF interval to an absolute value > 500 , two additional ECGs must be performed, within 30 minutes after the initial ECG (each with intervals at least 2 minutes apart).

If the average QTcF from the 3 ECGs is > 500 ms, the following actions should be taken:
Withhold study treatment. Repeat ECG triplicates hourly (± 15 minutes) until the average QTcF is ≤ 500 ms, or otherwise determined by consultation with a cardiologist or appropriate expert.

- Interrupt cabozantinib treatment.
- Hospitalize symptomatic subjects (eg, with palpitations, dizziness, syncope, orthostatic hypotension, a significant ventricular arrhythmia on ECG) for a thorough cardiology evaluation and management. Subjects with QTc prolongation and symptoms must be monitored closely until the QTc elevation and symptoms have resolved.
- Consider cardiology consultation for asymptomatic subjects for evaluation and management.
- Check electrolytes, especially magnesium, calcium, and potassium; correct abnormalities as clinically indicated
- Check concomitant medications for any medication that may have contributed to QT prolongation, and if possible, discontinue these medications (see <http://www.qtdrugs.org>)

Cabozantinib treatment may be restarted at a reduced dose level if all of the following conditions are met:

- Symptoms are determined to be unrelated to the QT interval prolongation
- The QTcF value > 500 ms is not confirmed.
- Study treatment has been interrupted through a minimum of 1 week following the return of the QTcF to ≤ 500 ms.
- QT prolongation can be unequivocally associated with an event other than cabozantinib administration and is treatable/has been resolved

Following reinitiation of study treatment, ECGs must be repeated weekly for 2 weeks (± 5 days), then every 2 weeks (± 5 days) for 1 month, then according to the protocol-defined time points.

Study treatment must be permanently discontinued if either of the following applies:

- Cardiac evaluation confirms that symptoms are the consequence of cabozantinib-related QT interval prolongation and cannot be addressed with dose interruption and/or reductions.
- Persistent recurrence of cabozantinib-related QTcF after reinitiation of study treatment after two dose reductions.

ELECTROLYTE DISORDERS Serum electrolyte disorders including hyponatremia, hypokalemia, hypomagnesemia, and hypophosphatemia have been reported during treatment with cabozantinib, and serum electrolyte levels should be monitored frequently while receiving cabozantinib. Standard clinical practice guidelines should be used for management of electrolyte disorders and may include oral or intravenous replacement. Clinically relevant electrolyte disorders should be managed according to the dose modification guidelines in the section 6.1.2.3.

THYROID FUNCTION DISORDERS

Preliminary data from ongoing studies indicate that treatment-emergent elevation of thyroid stimulating hormone (TSH) by cabozantinib may be dose-dependent. Currently available data are insufficient to determine the mechanism of TFT alterations and its clinical relevance. Routine monitoring of thyroid function and assessments for signs and symptoms associated with thyroid dysfunction is recommended before initiation and during treatment with cabozantinib. Management of thyroid dysfunction (eg, symptomatic hypothyroidism) should follow accepted clinical practice guidelines.

Other endocrine disorders such as hypocalcemia, hyperglycemia, and hypoglycemia, and associated laboratory changes, have been observed in single agent cabozantinib studies. Monitoring with standard laboratory tests for endocrine disorders and clinical examination prior to initiation and during treatment with cabozantinib is recommended. Cabozantinib should be discontinued in subjects with severe or life-threatening endocrine dysfunction.

HEMORRHAGIC EVENTS

Hemorrhagic events including serious and sometimes fatal events have been reported with cabozantinib. In order to mitigate risk of severe hemorrhage, subjects should be evaluated for potential bleeding risk factors prior to initiating cabozantinib treatment and monitored for bleeding events with serial complete blood counts and physical examination while on study. Risk factors for hemorrhagic events may include (but may not be limited to) the following:

- Tumor in the lung with cavitary lesions or tumor lesions which invade or encase major blood vessels. NSCLC with squamous cell differentiation is known for significant lung cavitations and centrally located tumors that may invade major blood vessels. Thus, the anatomic location and characteristics of tumor as well as the medical history must be carefully reviewed in the selection of subjects for treatment with cabozantinib.
- Recent or concurrent radiation.
- Active peptic ulcer disease, inflammatory GI diseases including Crohn's disease and ulcerative colitis
- Underlying medical conditions which affect normal hemostasis (eg, deficiencies in clotting factors and/or platelet function, or thrombocytopenia)
- Concomitant medication with anticoagulants or other drugs which affect normal hemostasis
- History of clinically significant hemoptysis, hematemesis, or hematuria

Cabozantinib should be discontinued in subjects with serious and life-threatening bleeding events or persistent, clinically significant hemoptysis or hematemesis

GI PERFORATION/FISTULA AND NON-GI FISTULA FORMATION

GI perforation/fistula and non-GI fistula formation have been reported with cabozantinib. Carefully monitor for episodes of abdominal pain, nausea, emesis, constipation, and fever especially in subjects with known risk factors for developing GI perforation/fistula or non-GI fistula, to allow for early diagnosis. Such risk factors include (but may not be limited to) the following:

- Intra-abdominal tumor/metastases invading GI or respiratory tract
- Active peptic ulcer disease, inflammatory bowel disease (ie, ulcerative colitis), diverticulitis, cholecystitis or symptomatic cholangitis, or appendicitis
- History of abdominal fistula, GI perforation, bowel obstruction, or intra-abdominal abscess
- Prior GI surgery (particularly when associated with delayed or incomplete healing). Complete healing following abdominal surgery or resolution of intra-abdominal abscess must be confirmed prior to initiating treatment with cabozantinib.

Additional risk factors include concurrent chronic use of steroid treatment or nonsteroidal anti-inflammatory drugs. Constipation indicative of bowel obstruction should be monitored and effectively managed.

OSTEONECROSIS

Osteonecrosis of the jaw (ONJ) has been reported with use of cabozantinib. Additional risk factors for ONJ have been identified such as use of bisphosphonates and denosumab, chemotherapy and anti-angiogenic drugs, use of corticosteroids, local radiotherapy, and dental or orofacial surgery procedures.

Osteonecrosis of the jaw (ONJ) can manifest as jaw pain, osteomyelitis, osteitis, bone erosion, tooth or periodontal infection, toothache, gingival ulceration, or gingival erosion. Persistent pain or slow healing of the mouth or jaw after dental surgery may also be manifestations of ONJ.

Performing an oral examination is recommended prior to initiation of cabozantinib and periodically during cabozantinib therapy. Advise patients regarding oral hygiene practice and to quickly report symptoms to investigator. Caution should be used in patients receiving bisphosphonates.

Invasive dental procedures should be avoided. In cases where dental procedures are unavoidable, treatment with cabozantinib should be held for approximately 4 weeks prior (+/- 7 days) to a dental procedure and resumed after complete healing has occurred.

Subjects with any documented case of osteonecrosis should have study treatment interrupted, and appropriate clinical management should be initiated. Re-initiation of study treatment must be discussed with and approved by Exelixis on a case-by-case basis.

6.2.2 PEMBROLIZUMAB:

DIARRHEA:

Patients should be carefully monitored for signs and symptoms of enterocolitis (such as diarrhea, abdominal pain, blood or mucus in stool, with or without fever) and of bowel perforation (such as peritoneal signs and ileus). In symptomatic patients, infectious etiologies should be ruled out, and if symptoms are persistent and/or severe, endoscopic evaluation should be considered.

- In patients with severe enterocolitis, permanent discontinuation of pembrolizumab should be considered and treatment with systemic corticosteroids should be initiated at a dose of 1 to 2 mg/kg/day of prednisone or equivalent. When symptoms improve to Grade 1 or less, corticosteroid taper should be started and continued over at least 1 month.
- In patients with moderate enterocolitis, pembrolizumab should be withheld and anti-diarrheal treatment should be started. If symptoms are persistent for more than one week, systemic corticosteroids should be initiated (e.g., 0.5 mg/kg/day of prednisone or equivalent). When symptoms improve to Grade 1 or less, corticosteroid taper should be started and continued over at least 1 month.
- All patients who experience diarrhea should be advised to drink liberal quantities of clear fluids. If sufficient oral fluid intake is not feasible, fluid and electrolytes should be substituted via IV infusion.

NAUSEA/VOMITING

Nausea and vomiting should be treated aggressively, and consideration should be given in subsequent cycles to the administration of prophylactic antiemetic therapy according to standard institutional practice. Patients should be strongly encouraged to maintain liberal oral fluid intake.

ANEMIA:

Transfusions may be utilized as clinically indicated for the treatment of anemia but should be clearly noted as concurrent medications.

NEUTROPENIA:

Prophylactic use of colony-stimulating factors including Granulocyte Colony-Stimulating Factor (G-CSF), pegylated G-CSF or Granulocyte Macrophage Colony-Stimulating Factor GM-CSF is not allowed in this study. Therapeutic use of G-CSF is allowed in patients with Grade 3-4 febrile neutropenia.

THROMBOCYTOPENIA:

Transfusion of platelets may be used if clinically indicated. ITP should be ruled out before initiation of platelet transfusion.

ANTI-INFECTIVES:

Patients with a documented infectious complication should receive oral or IV antibiotics or other anti-infective agents as considered appropriate by the treating Investigator for a given

infectious condition, according to standard institutional practice.

IMMUNE-RELATED ADVERSE EVENTS:

Patients who develop a G2 or higher irAE (e.g., colitis, skin rash, hepatitis, uveitis, hypo- or hyperthyroidism, hypophysitis, or any other), should be discussed immediately with the SPONSOR. Depending on the type and severity of an irAE, oral or intravenous treatment with a corticosteroid should be considered, in addition to appropriate symptomatic treatment of a given condition.

PNEUMONITIS:

Subjects with symptomatic pneumonitis should immediately stop receiving pembrolizumab and have an evaluation. The evaluation may include bronchoscopy and pulmonary function tests to rule out other causes such as infection. If the subject is determined to have study drug associated pneumonitis, the suggested treatment plan is detailed in table below:

For Grade 2 pneumonitis that improves to \leq Grade 1 within 12 weeks, the following rules should apply:

- First episode of pneumonitis
 - Improvement occurs in \leq 2 weeks-dose of pembrolizumab, keep the same dose.
 - May increase dosing interval by one week in subsequent cycles if improvement occurs $>$ 2 weeks.
- Second episode of pneumonitis – permanently discontinue pembrolizumab if upon rechallenge subject develops pneumonitis \geq Grade 2.

Table 9: Approach to Pneumonitis from pembrolizumab

Study drug associated pneumonitis	Treatment	Supportive care
Grade 1 (asymptomatic)	No action	Intervention not indicated
Grade 2	Withhold pembrolizumab, may return to treatment if improves to grade 1 or resolves within 12 weeks	Systemic corticosteroids are indicated. Taper if necessary.
Grade 3 and Grade 4	Discontinue pembrolizumab.	Systemic corticosteroids are indicated.

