4.3 JUSTIFICATION FOR DOSE

4.3.1 PHASE 1B:

The Dose Escalation Phase 1b part will utilize a "3+3" design for escalation. The study plan includes the evaluation of 3 planned dose levels of cabozantinib administered orally. A minimum of 6 and a maximum of 18 subjects will be enrolled in each dose escalation cohort in Phase 1b, starting at 40 mg daily. The Sponsor reserves the right to adjust the planned cabozantinib dose levels based on emerging study data (Note: This will be considered as a protocol amendment) The planned cabozantinib dose levels to be studied in the Dose Escalation Phase 1b are presented in table 1. If the MTD has not been identified at the highest planned dose level, the Sponsor reserves the right to consider additional dose levels, and this would require a protocol amendment.

Table 1: Planned Dose Levels of Cabozantinib and Pembrolizumab

Dose Level	Cabozantinib	Pembrolizumab
-1	20 mg	200 mg
0 (starting dose)	40 mg	200 mg
1	60 mg	200 mg

Pembrolizumab will be administered at a standard recommended (drug label) dosing of 200 mg intravenously once every 3 weeks.

DLTs are defined in Section 4.3.2 Part 1 Dose Escalation: Dose-Limiting Toxicities (DLTs). The DLT rate across all subjects enrolled within a cohort in phase 1 must be <33% to allow escalation to the next dose level in that Arm. *The DLT observation period is 21 DAYS from date of first dose of cabozantinib.*

At the start of any new cohort, there will be a waiting period of at least 1 week after the first dose of the 3rd subject before enrollment of additional subjects into the same cohort. If a subject withdraws from the study prior to completion of the DLT assessment period for a reason other than a DLT, a replacement subject will be enrolled in that cohort.

Dose escalation in Part 1 to the next dose level can only occur after a minimum of 3 subjects have completed their DLT observation period for the current dose level, and the DLT rate does not exceed 33%.

Prior to escalation to a new dose level, the Safety Review Committee (SRC) will meet to review the safety data from the current cohort in order to determine if dose escalation is warranted.

The following rules govern dose escalation in Phase 1b:

- If none of the initial 3 subjects at a dose level experiences a DLT, escalation to the next dose level may occur. However, the Sponsor reserves the right to enroll up to 12 subjects in a cohort in order to obtain additional safety information.

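### Section 6.2.1: the QTc hold, restart and permanent-stop rules for cabozantinib contradict each other and need to be reconciled

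*Combined protocol and SAP*

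**What the plan says.** All of the following is in the combined protocol and SAP, section 6.2.1, under corrected QTc prolongation, unless another place is named.

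- **Repeat ECGs.** After a single on-study QTcF above 500 ms, "two additional ECGs must be performed, within 30 minutes after the initial ECG".
- **Hold.** "If the average QTcF from the 3 ECGs is > 500 ms, the following actions should be taken". Among the actions: "Interrupt cabozantinib treatment". Triplicates are then repeated hourly until the average is back at or below 500 ms, or as decided with a cardiologist or other expert.
- **Restart.** "Cabozantinib treatment may be restarted at a reduced dose level if all of the following conditions are met". There are four conditions: (1) symptoms are judged unrelated to the QT prolongation; (2) "The QTcF value > 500 ms is not confirmed"; (3) treatment has stayed off for at least 1 week after QTcF came back to 500 ms or below; (4) "QT prolongation can be unequivocally associated with an event other than cabozantinib administration and is treatable/has been resolved".
- **After restart.** An ECG schedule is laid down for patients who resume.
- **Permanent stop.** Either of two criteria suffices. The first is that symptoms are shown to result from cabozantinib-related prolongation and cannot be dealt with by interrupting or reducing the dose. The second is "Persistent recurrence of cabozantinib-related QTcF after reinitiation of study treatment after two dose reductions".
- **Dose levels.** Table 1 in section 4.3.1 lists 20, 40 and 60 mg. The Phase 1b starting row reads "0 (starting dose) 40 mg 200 mg".

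**The concern.** A hold rule, a restart rule and a stop rule for the same event should fit together: each held patient should have a defined route back or a defined route out. Here the condition for leaving the hold appears to negate the condition for entering it, and the restart and stop rules take opposite positions on whether a cabozantinib-related event can be followed by a restart.

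This is a cardiac safety rule. If it can be read in two ways, one investigator may treat a confirmed, drug-related prolongation as ending cabozantinib because the joint list cannot be met. A colleague may restart because the later text plainly expects restarts. Cabozantinib exposure and recorded reasons for discontinuation would then depend partly on who read the rule.

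**Working it through.** The plan gives no figure to reproduce. The check sets the rules side by side.

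**Step 1. Trigger against restart condition 2.** The three-ECG average is the only step the documents give for verifying a single high reading. Section 5.2, item 25, uses it in the same way to settle eligibility. If C denotes an average above 500 ms, the hold requires C. If 'confirmed' means C, condition 2 requires not-C, and the two cannot both hold.

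**Step 2. Condition 2 against condition 3.** Condition 3 counts a week from the return of QTcF to 500 ms or below. That presupposes the elevation which condition 2 says was not confirmed, yet both are required.

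**Step 3. Condition 4 against the stop criteria.**

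| Rule | Position on cabozantinib-related prolongation |
|---|---|
| Restart condition 4 | Restart only if the cause is unequivocally something else |
| First stop criterion | Stop only if interruption or reduction cannot deal with it, so some cases are expected to be manageable |
| Second stop criterion | Stop if it persistently recurs after restart and two reductions, so restart after such an event is expected |

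A patient whose prolongation is caused by cabozantinib and settles during the hold fails condition 4. If it can be managed by interruption or reduction and has not recurred, that patient meets neither stop criterion. Section 6.2.1's QTc rules then neither permit restart nor require a stop. This step does not use the word 'confirmed'.

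**Step 4. Dose levels.** Assuming the Table 1 levels are the reduction ladder:

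- from 60 mg: 40, then 20, giving two lower levels;
- from 40 mg: 20, giving one;
- from 20 mg: none listed, so restart at a reduced level has no defined level either.

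Section 6.1.2.3 allows re-escalation at the investigator's discretion, except after certain Grade 4 events. A course of 40 to 20 to 40 to 20 mg contains two reductions, so two reductions from 40 mg are possible.

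**Step 5. Is condition 2 strictly impossible for a held patient?** Take illustrative readings, not from the documents, of 560, 480 and 480 ms. The mean is (560 + 480 + 480) / 3 = 1520 / 3 = 506.7 ms, so the hold applies. Neither repeat exceeds 500 ms. If 'confirmed' means that the repeats show it again, this patient meets condition 2 and can go on to meet condition 3.

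**Step 6. Does the restart wording change the Phase 1b dose-intensity DLT criterion?** Section 4.3.2 uses a 21-day window and a 75% threshold. A patient who restarts inside the window has been off at least a week:

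- 7 missed daily doses leave 14/21 = 67%;
- if the day count gives only 6, 15/21 = 71%.

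Both are below 75% before any dose reduction is counted. If the hold begins too late for a restart inside the window, the restart rule has no bearing on it.

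**The case against.** The strongest reply is that the QTc text is loosely worded guidance with enough around it to be safe. Section 6.2 opens by describing its content as general guidelines and leaves management to the treating provider. The restart sentence is permissive. Other routes to stopping exist: unacceptable adverse experiences and repeated dose delays for the same toxicity (section 7.1), inability to tolerate cabozantinib (section 7.2), and the Grade 4 row of Table 4. 'Confirmed' is undefined and might refer to the repeat readings, the later hourly triplicates or the expert consultation.

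Much of this stands, and it rules out four stronger readings that a reader might infer:

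- **That no held patient can ever restart.** This needs 'confirmed' to mean exactly the three-ECG average. The documents do not say so, and the 506.7 ms example shows a reading under which condition 2 can be met.
- **That a patient starting at 40 mg can never meet the two-reductions criterion.** Re-escalation makes it possible. Table 1 is an escalation table, section 6.1.2.3 leaves the Phase 2 modification criteria to be finalized, and further levels may be added by amendment.
- **That the restart wording decides the DLT dose-intensity result.** The 1-week minimum already puts a patient who restarts inside the window below 75%. The regular on-treatment ECGs, every 12 weeks in section 1.3 or monthly in section 6.2.1, would not usually detect an event within 21 days.
- **That sites would diverge.** This is a single-center trial, so the divergence can only be between investigators.

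What the reply does not remove is the attribution conflict, which holds on any reading of 'confirmed'. Nor does a guideline label make the rule coherent, since the stop criteria are themselves written as mandatory.

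**Conclusion.** Wrong as written. The hold trigger and the second restart condition conflict on their plain reading. The second and third restart conditions sit badly together. The attribution condition for restart contradicts what both permanent-stop criteria assume. The last of these is the firmest because it needs no assumption about undefined terms.

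The poor fit of the two-reductions wording is conditional. It rests on treating Table 1 as the reduction ladder, which the documents do not state, though they give no other. On that assumption there are two, one and no lower levels from 60, 40 and 20 mg, and the criterion is awkward rather than impossible from 40 mg, since re-escalation may occur.

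The practical consequence is inconsistent handling of the same ECG by investigators at one center, limited by the guideline status of section 6.2 and the other stopping routes. The documents give no rate of QTcF above 500 ms, so the number of patients affected cannot be estimated. Sample size, error rates and the primary response test are unaffected.

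**What to change.** The clinical team should reconcile the QTc text in section 6.2.1 so that:

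- 'confirmed' is defined in relation to the three-ECG average and the later repeat triplicates;
- an unconfirmed single high reading and an average above 500 ms have separate, stated pathways;
- each restart condition is marked as required jointly or as an alternative;
- the attribution condition for restart agrees with the permanent-stop criteria, and a held patient who meets neither has a stated route;
- the two-reductions wording matches the dose levels that exist for each starting dose, with the reduction ladder named and the effect of re-escalation on the count stated.

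Which clinical rule or dose applies is for the clinical team; none is proposed here. The cost is an amendment to the wording of one subsection, with no added procedures and no change to the design or analysis.
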